| CGIC   |                 |                 |                    |           |    |    | X  |     | X (V9
only) |     |     |     |     |     | X   |     |     |     |     |     |     |     |     |                  |     |     |     |     |     |     |     |     |     |
| Asthma
Daily Diary
including
home peak
expiratory          |                 | X               | X                  | X         | X  | X  | X  | X   | X              | X   | X   | X   | X   | X   | X   | X   | X   | X   | X   | X   | X   | X   | X   | X                | X   | X   | X   | X   | X   |     |     |     |     |

 AQLQ (S) +12 performed at the site unless completed at home the day prior.

| Assessment/
activity                            | Enroll-
ment | Run-
in      | Random-
ization | Treatment |    |    |    |                 |     |     |     |     |     |     |     |     |     | EOT | FU  | FU  | UN  |     |     |     |     |     |     |     |     |     |                 |                 |     |     |     |     |                 |     |   |   |
|--|-----------------|-----------------|--------------------|-----------|----|----|----|-----------------|-----|-----|-----|-----|-----|-----|-----|-----|-----|-----|-----|-----|------------------|-----|-----|-----|-----|-----|-----|-----|-----|-----|-----------------|-----------------|-----|-----|-----|-----|-----------------|-----|---|---|
|  |                 |                 |                    | V1        | V2 | V3 | V4 | V5              | V6  | V7  | V8  | V9  | V10 | V11 | V12 | V13 | V14 |     |     |     |                  | V15 | V16 | V17 | V18 | V19 | V20 | V21 | V22 | V23 | V24             | V25             | V26 | V27 | V28 | V29 | V30             | V31 |   |   |
|  | V1  | V2  | V3                 | w2        | w4 | w6 | w8 | w10             | w12 | w14 | w16 | w18 | w20 | w22 | w24 | w26 | w28 | w30 | w32 | w34 | w36              | w38 | w40 | w42 | w44 | w46 | w48 | w50 | w52 | w56 | w72             |                 |     | IPD |     |     |                 |     |   |   |
|  | w-6 to
-4    | w-2             | w0                 |           |    |    |    |                 |     |     |     |     |     |     |     |     |     |     |     |     |                  |     |     |     |     |     |     |     |     |     |                 |                 |     |     |     |     |                 |     |   |   |
| Visit window (days)                    |                 |                 |                    |           |    |    |    |                 |     |     |     |     |     |     |     |     |     |     |     |     |                  |     |     |     |     |     |     |     |     |     |                 |                 |     |     |     |     |                 |     |   |   |
|  | N/A             | -3              | N/A                | ±3        | ±3 | ±3 | ±3 | ±3              | ±3  | ±3  | ±3  | ±3  | ±3  | ±3  | ±3  | ±3  | ±3  | ±3  | ±3  | ±3  | ±3               | ±3  | ±3  | ±3  | ±3  | ±3  | ±3  | ±3  | ±3  | +7  | +7              | N/A             | N/A |     |     |     |                 |     |   |   |
| flow
assessment
adherence                    |                 |                 |                    |           |    |    |    |                 |     |     |     |     |     |     |     |     |     |     |     |     |                  |     |     |     |     |     |     |     |     |     |                 |                 |     |     |     |     |                 |     |   |   |
| Spirometry,
ePRO and
ePEF device
training | X               | X               |                    |           |    |    |    |                 |     |     |     |     |     |     |     |     |     |     |     |     |                  |     |     |     |     |     |     |     |     |     |                 |                 |     |     |     |     |                 |     |   |   |
| Pre-BD,
Spirometry                              | X               | X               | X                  | X         | X  | X  | X  | X  | X   |     |     |     |     |     |     | X   |     |     |     |     |                  |     |     |     |     |     |     |     |     |     | X               | X               | X   |     |     |     | X               |     |   |   |
| Post-BD,
Spirometry                             |                 | X               | X                  |           |    |    |    |                 |     |     |     |     |     |     |     |     |     |     |     |     |                  |     |     |     |     |     |     |     |     |     | X  | X  |     |     |     |     | X  | X   |   |   |
| PK   |                 |                 | X                  | X         |    |    | X  |                 |     |     |     |     |     |     |     | X   |     |     |     |     |                  |     |     |     |     |     |     |     |     | X   | X               |                 |     |     |     |     |                 |     |   |   |
| ADA/nAb  |                 |                 | X                  |           |    |    |    |                 |     |     |     |     |     |     |     | X   |     |     |     |     |                  |     |     |     |     |     |     |     |     |     | X               | X               |     |     |     |     |                 |     |   |   |
| FE NO                                   | X               |                 | X                  | X         |    |    | X  |                 |     |     |     |     |     |     |     | X   |     |     |     |     |                  |     |     |     |     |     |     |     |     |     | X               |                 |     |     |     |     |                 |     |   |   |
| Assessment
of asthma
exacerbations           | X               | X               | X                  | X         | X  | X  | X  | X               | X   | X   | X   | X   | X   | X   | X   | X   | X   | X   | X   | X   | X                | X   | X   | X   | X   | X   | X   | X   | X   | X   | X               | X               | X   | X   | X   | X   | X               | X   | X | X |
| Randomization                                      |                 |                 | X                  |           |    |    |    |                 |     |     |     |     |     |     |     |     |     |     |     |     |                  |     |     |     |     |     |     |     |     |     |                 |                 |     |     |     |     |                 |     |   |   |

 Pre-BD Spirometry only at visit 9 and not at visit 10

 Post-BD, Spirometry on Visit 7, Visit 29 (EOT) and IPD Visit: Only step 1 of the reversibility assessment (section 5.1.2.1) is required.

| Assessment/
activity                         | Enroll-
ment | Run-
in      | Random-
ization | Treatment                        |    |    |    |     |     |     |     |     |     |     |     |     |     |     |     |     | EOT | FU  | FU  | IPD | UNS  |     |     |     |     |     |     |     |     |
|---|-----------------|-----------------|--------------------|----------------------------------|----|----|----|-----|-----|-----|-----|-----|-----|-----|-----|-----|-----|-----|-----|-----|-----|-----|-----|-----|-------------------|-----|-----|-----|-----|-----|-----|-----|-----|
|   |                 |                 |                    | V4                               | V5 | V6 | V7 | V8  | V9  | V10 | V11 | V12 | V13 | V14 | V15 | V16 | V17 | V18 | V19 | V20 |     |     |     |     |                   | V21 | V22 | V23 | V24 | V25 | V26 | V27 | V28 |
|   |                 |                 |                    | w2                               | w4 | w6 | w8 | w10 | w12 | w14 | w16 | w18 | w20 | w22 | w24 | w26 | w28 | w30 | w32 | w34 |     |     |     |     |                   | w36 | w38 | w40 | w42 | w44 | w46 | w48 | w50 |
|   | V1  | V2  | V3                 | Visit window (days)  |    |    |    |     |     |     |     |     |     |     |     |     |     |     |     |     | V29 | V30 | V31 |     |                   |     |     |     |     |     |     |     |     |
|   | w-6 to
-4    | w-2             | w0                 |                                  |    |    |    |     |     |     |     |     |     |     |     |     |     |     |     |     |     |     |     |     |                   |     |     |     |     |     |     |     |     |
|   | N/A             | -3              | N/A                | ±3                               | ±3 | ±3 | ±3 | ±3  | ±3  | ±3  | ±3  | ±3  | ±3  | ±3  | ±3  | ±3  | ±3  | ±3  | ±3  | ±3  | ±3  | ±3  | ±3  | ±3  | ±3                | ±3  | ±3  | +7  | +7  |     |     |     |     |
| Administration
of IP                         |                 |                 | X                  | X                                | X  | X  | X  | X   | X   | X   | X   | X   | X   | X   | X   | X   | X   | X   | X   | X   | X   | X   | X   | X   | X                 | X   | X   | X   | X   |     |     |     |     |
| Adverse
events                               | X               | X               | X                  | X                                | X  | X  | X  | X   | X   | X   | X   | X   | X   | X   | X   | X   | X   | X   | X   | X   | X   | X   | X   | X   | X                 | X   | X   | X   | X   |     |     |     |     |
| Concomitant
medications                      | X               | X               | X                  | X                                | X  | X  | X  | X   | X   | X   | X   | X   | X   | X   | X   | X   | X   | X   | X   | X   | X   | X   | X   | X   | X                 | X   | X   | X   | X   |     |     |     |     |
| Blood sample
for perostin                    |                 | X               | X                  |                                  |    |    |    |     |     |     |     |     |     |     |     |     |     |     |     |     |     |     |     |     |                   |     |     |     |     |     |     |     |     |
| Blood sample
DPP4 and
other
biomarkers |                 | X               | X                  |                                  |    |    |    |     |     |     |     |     |     |     |     |     |     |     |     |     |     |     |     |     |                   |     |     |     |     |     |     |     |     |
| Blood
sample for
DNA
(optional)        | X  |                 |                    |                                  |    |    |    |     |     |     |     |     |     |     |     |     |     |     |     |     |     |     |     |     |                   |     |     |     |     |     |     |     |     |

ADA = anti-drug antibodies; AE=Adverse event; ACQ-6=Asthma Control Questionnaire 6; ADA=Anti-drug antibodies; AQLQ(S)+12=Standardised Asthma Quality of Life Questionnaire for 12 Years and Older; β-HCG=Beta Human Chorionic Gonadotropin; BD=Bronchodilator; DNA=Deoxyribonucleic acid; DPP4=Dipeptidyl Peptidase-4; dECG=digital electrocardiogram; EOT =End of Treatment; ePRO=electronic Patient Reported Outcome device; FENO=Fractional Exhaled Nitric Oxide; FSH= Follicle-stimulating hormone; HIV=Human immunodeficiency virus; IgE=Immunoglobulin E; IPD= Investigational product discontinuation; nAb=Neutralizing antibodies; PK=Pharmacokinetic; PRO=Patient Reported Outcome

 Blood sample for DNA may be collected at any visit after visit 1, only after the subject has signed a separate consent.  
 UNS (Unscheduled Visit): At unscheduled visits for assessing an asthma exacerbation, the following assessments must be performed. For other unscheduled visits assessments may be performed per investigator's judgement.

## 4.1 Enrolment/run-in period

### 4.1.1 Enrolment (Visit 1)

Each potential subject who is at, or over the age of majority (as per local law) will provide informed consent prior to the start of any study specific procedures and undergo assessments applicable for this visit (see [Table 1](#)).

For subjects less than the age of majority, in addition to the subject providing informed assent, the subject's legal guardian must also provide their informed consent.

With the exception of documentation of informed consent and assent (if applicable), which can be completed up to 30 days prior to Visit 1, all other Visit 1 procedures should be completed within a 1 to 3-working day window. The 3-day window is to enable subjects to return if necessary for the spirometry assessments on a morning when they have had their BD medications withheld in accordance with the spirometry instructions (see section [5.1.2](#)). The registration of the subject's enrollment via IWRS/IVRS should occur on the day when the Visit 1 procedures are performed.

Visit 1 assessments are primarily concerned with assessing the subject's eligibility (inclusion/exclusion) criteria, including their asthma disease state, the requisite level of severity based on maintenance medications, exacerbation history, and the current level of control based on an initial ACQ-6 score.

Spirometry will also be performed at Visit 1. Subjects must have a pre-BD FEV1 value <80% of their PNV (<90% for subjects 12 to 17 years of age) in order to proceed in the study (as per Section [3.1](#), criterion [8](#)). If not, the subject will be screen failed.

Other study assessments and procedures to be performed at this visit include the recording of the subject's demographics, a complete physical examination (including height and weight), vital signs, a dECG, recording the subject's medical/surgical history and concomitant medications, collection of blood samples for haematology/clinical chemistry, serology and biomarkers, collection of a urine sample for urinalysis, and a pregnancy test for WOCBP.

A record of physician-diagnosed asthma, ICS-LABA use, use of other asthma controllers (Section [3.1](#), criteria [5](#), [6](#) and [7](#)) and asthma exacerbations over the prior year (Section [3.1](#), criterion [10](#)) is required for source documentation. A subject's verbal history suggestive of asthma symptoms and/or prior asthma exacerbations, but without supporting documentation, is **not** sufficient to satisfy these inclusion criteria.

### 4.1.2 Run-in (Visit 2)

The run-in period (i.e., from Visit 1 to Visit 3) is 4 to 6 weeks (with a 3 day window) in duration. The subject should remain on their current asthma treatment with no changes

throughout the entire run-in period. Assessments applicable for the run-in period are listed in [Table 1](#).

Visit 2 is primarily concerned with evaluating whether lung function meets the respective study eligibility criteria, to collect AE and concomitant medication information, as well as a blood sample for periostin (to be used for stratification at randomization).

The protocol specified reversibility criterion (i.e. inclusion criterion 9) will be assessed at this visit. Should this criterion not be met at Visit 2, subjects must fulfill it at Visit 3 in order to be randomised.

The subject will be supplied with an electronic hand-held spirometer (peak flow meter) to measure the subject's PEF at home, and an ePRO device to record asthma symptoms and complete relevant questionnaires (see section 5.2.2 for further details).

Visit 2 may be performed as a telephone visit (for collection of SAE information only) if the subject is confirmed as ineligible for the study (e.g., based on laboratory results from Visit 1, or medical history).

The subject's eligibility should be evaluated at each visit during the run-in period with the relevant documentation entered in the source and eCRF.

#### **4.1.3 Randomization (Visit 3)**

Lung function with measurement of morning pre-dose, pre-BD and post-BD FEV1 will be performed on Visit 3 prior to randomization. Subjects should have a morning pre-BD FEV1 of  $\geq 40\%$  and  $< 80\%$  ( $< 90\%$  for subjects 12 to 17 years of age) of the subject's PNV, and fulfil the protocol-specified reversibility criterion ( $\geq 12\%$  FEV1 and  $\geq 200$  mL), if either is not met at Visit 2. Other inclusion criteria at randomization will be confirmed at Visit 3. Before randomization the subject's compliance with their usual asthma controller (ICS-LABA), and any other asthma controller medication, and ePRO completion must be confirmed (see section 3.1, inclusion criteria 18 and 19). The subject should bring the ePRO device to this visit where they will complete the ACQ-6, AQLQ(S)+12, EQ-5D-5L, and the WPAI + CIQ.

If the periostin value measured at Visit 2 is missing at randomization (Visit 3), the subject should not be randomized, nor should any Visit 3 assessments be performed. A new blood sample for periostin should be taken at this visit and a new Visit 3 visit should be re-scheduled to occur 2 weeks later, along with all other Visit 3 assessments.

#### **4.1.4 Re-screening**

Subjects who experience an asthma exacerbation within 30 days prior to ICF date or during the screening/run-in phase should be screen failed. They may be re-screened no sooner than 30 days after their last dose of systemic steroids.

Subjects with respiratory infections requiring antibiotics or antiviral medication within 30 days prior to the date informed consent is obtained or during the screening/run-in period may also be re-screened.

Re-screening for the above mentioned reasons is allowed only once for the subject. Subjects should be re-screened no later than 3 months failing initial enrolment.

If the reason for screen failure was transient (including but not limited to study-supplied equipment failure and unforeseen personal events that mandate missed screening visits), subjects may potentially be re-screened. These cases should be discussed with the AstraZeneca Study Physician and documented approval for re-screening should be filed in the Investigator Study File (ISF).

**Re-screening for subjects who have screen-failed due to an ACQ score <1.5 is not allowed.**

Any re-screened subject will be re-enrolled and reassigned their originally assigned enrolment number after signing a new Informed Consent Form (ICF), or assent form, and after all run-in assessments have been performed as listed in [Table 1](#) (with the exception of testing for HIV1 an HIV2, hepatitis B and C, and FSH). Re-enrolment is only allowed once for any subject, regardless of whether this is due to an exacerbation or infection. The subject may not be re-screened if any other eligibility criteria are failed.

## **4.2 Treatment period**

Inclusion criteria at randomization will be confirmed at Visit 3. Before randomization the subject's compliance with their usual asthma controller ICS-LABA and other asthma controller medication, and ePRO completion must be confirmed (see section [3.1](#), inclusion criteria [18](#) and [19](#)).

Subjects confirmed as eligible will be randomized at Visit 3 (Week 0) in a 1:1 ratio (i.e. 385 subjects on tralokinumab, and 385 subjects on placebo). Subjects will be administered tralokinumab 300mg or placebo via subcutaneous injection at the study site Q2W for a total of 26 doses.

The first dose of the IP will be administered following randomization through IWRS/IVRS at Visit 3.

Following randomization the subject will receive 52 weeks of double-blind treatment, with the last dose of tralokinumab/placebo administered at Visit 28 (Week 50).

Subjects will have scheduled visits at 2-week intervals to complete protocol-specific assessments and IP administration, as listed in [Table 1](#). Restrictions as set out in section [7.7.2](#) will continue to apply throughout the treatment period. In case of an asthma worsening/exacerbation (see section [5.1.1](#)), subjects should be evaluated at the study site,

when feasible, at an unscheduled visit, or ordinary visit if the worsening happens to fall within a scheduled visit window.

Subjects will continue to measure their PEF at home, as well as record asthma symptoms and responses to questionnaires in the Asthma Daily Diary throughout the 52-week treatment period (see section 5.2.2 for details).

Subjects will have brief physical exams performed at times listed in Table 1. A complete physical exam will be performed at Visit 29 (Week 52).

Additional blood samples will be obtained from the subjects at Visits 3, 9, 16 and 29 to further explore the relationship between the clinical response of tralokinumab and biomarkers.

The subject's adherence for completing all questionnaires in the ePRO will be assessed at all visits during the treatment period, with retraining provided as required.

At Week 52 subjects will come to the site for the End of Treatment (EOT) visit. The subject should bring the ePRO device to the EOT visit and complete the ACQ-6, AQLQ(S)+12, EQ-5D-5L, and the WPAI + CIQ, unless they have been completed at home prior to the visit.

The final follow up visits (i.e., 30 and 31) are to occur 4 weeks (+7 days) and 20 weeks (+7 days) from the date of the EOT visit, respectively.

Subjects who prematurely discontinue IP (see section 3.9) should return to the study site and complete procedures described for the IP Discontinuation Visit (IPD visit), see Table 1.

At the IP discontinuation visit, the subject will be given three options as to how they will be followed up:

1. Ideally, the subject should return for all regular clinic visits and perform all scheduled assessments until he/she completes a total of 52 weeks in the study, or,
2. The subject will be followed up on a monthly basis via telephone calls while continuing eDiary completion, until the subject completes 52 weeks in the study. No further procedures will be performed. Or,
3. The subject will be contacted at 52 weeks post randomization. No other study assessments will be performed prior to this contact.

For each option, an EOT visit will be conducted.

For option 1, all procedures will be done at each visit as indicated in Table 1. For options 2 and 3, AEs/SAEs, changes in concomitant medications and asthma exacerbation information are the minimum elements that must be collected at each contact.

The subject's decision needs to be documented in the eCRF and the specific section in the ICF/assent form addendum needs to be signed by the subject.

Should the subject choose option 2 or 3 above, they will complete the IP Discontinuation visit immediately and then a follow up telephone call at week 52. If the subject chooses option 1, they will complete the IP Discontinuation visit immediately and then the EOT visit at week 52. The EOT visit/call will be completed immediately in the case of early withdrawal from option 1 or 2.

Subjects who initially chose options 1 or 2 and subsequently cannot or do not wish to comply with the requirements of the chosen option, can choose to continue with a less invasive option (i.e.: Subject initially choosing option 1 can continue with 2 or 3, subjects initially choosing option 2 can continue with 3).

Subjects who do not wish to have any follow up contacts at all, will be discontinued from the study. All discontinued subjects must return the ePRO and ePEF devices at the EOT visit.

Completion, or early termination of IP treatment, will be registered via the IWRS/IVRS for each subject.

### **4.3 Follow-up period**

Subjects will have follow-up visits (30 and 31) at Weeks 56 and 72, respectively.

## **5. STUDY ASSESSMENTS**

The Rave Web Based Data Capture (WBDC) system will be used for data collection and query handling. The investigator will ensure that data are recorded on eCRFs as specified in the study protocol and in accordance with the instructions provided.

The investigator will ensure the accuracy, completeness, and timeliness of the data recorded and of the provision of answers to data queries according to the Clinical Study Agreement. The investigator will sign the completed eCRFs. A copy of the completed eCRFs will be archived at the study site upon completion of the study.

### **5.1 Efficacy assessments**

#### **5.1.1 Assessment of asthma exacerbations**

For the purpose of the protocol, an asthma exacerbation will be defined as a worsening of asthma that leads to any of the following:

- Use of systemic corticosteroids for at least 3 days; a single depo-injectable dose of corticosteroids will be considered equivalent to a 3-day course of systemic corticosteroids

- An ER or urgent care visit (defined as evaluation and treatment for <24 hours in an ED or urgent care center) due to asthma that required systemic corticosteroids (as per above)
- An inpatient hospitalization (defined as admission to an inpatient facility and/or evaluation and treatment in a healthcare facility for  $\geq 24$  hours) due to asthma

The ePRO device will be programmed to alert both the subject and study site when certain pre-specified worsening thresholds are crossed as follows:

- Decrease in morning peak flow  $\geq 30\%$  on at least 2 of 3 successive days compared with baseline (last 10 days of run-in), and/or
- A  $\geq 50\%$  increase in rescue medication or one new or additional nebulized  $\beta_2$ -agonist on at least 2 of 3 successive days compared with the average use for the previous week, and/or
- Nocturnal awakening due to asthma requiring rescue medication use for at least 2 of 3 successive nights, and/or;
- An increase in total asthma symptom score (the sum of day time [evening assessment] and night-time [morning assessment] of at least 2 units above the run-in average (last 10 days of run-in), or the highest possible score (daily score of 6), on at least 2 of 3 successive days.

For the purpose of the protocol, worsening of asthma is defined as new or increased symptoms and/or signs (i.e., physical examination or lung function) that can be either concerning to the subject (subject-driven) or related to an Asthma Daily Diary alert (diary-driven).

If an exacerbation event is not associated with deterioration in at least one of the pre-specified subject-driven and/or diary-driven objective measurements, the Investigator will have to justify the decision for defining the event as an exacerbation. Events that are not supported by any objective assessment will be deemed not to be a protocol-defined exacerbation.

In order to calculate the number of exacerbations experienced by a subject during the 52-week treatment period, the following rule will be applied:

- The start of an exacerbation is defined as the start date of systemic corticosteroids, ER or urgent care visit requiring systemic corticosteroids, or hospital admission due to asthma, whichever occurs earlier, and the end date is defined as the last day of systemic corticosteroids or ER or urgent care visit or hospital discharge, whichever occurs later.

Additional systemic corticosteroid treatments, ER or urgent care visits requiring use of systemic corticosteroids, or inpatient hospitalization due to asthma occurring during an exacerbation should not be regarded as a new exacerbation. In order to be counted as a new exacerbation it must be preceded by at least 7 days in which neither criterion is fulfilled.

The subject may remain in the study after an exacerbation and continue to receive IP if the Investigator judges that it is medically appropriate for the subject to do so.

Reasonable attempts should be made by the Investigator to bring the subject into the study site for evaluation of a diary alert or subject initiated asthma worsening, particularly when it results in additional treatment being prescribed. Study site evaluations for asthma worsening may occur as an unscheduled visit or as part of an ordinary site visit if the worsening happens to be coincident with a scheduled visit window.

A copy of the medical record should be obtained for exacerbations evaluated and treated at non-study sites (e.g., by the primary care HCP or at an ED/hospital) and details entered into the exacerbation eCRF module in a timely fashion. Changes in concomitant medication due to exacerbation must be recorded in the appropriate module of the eCRF.

Maximum follow-up time for a subject is approximately 52 weeks; defined as the time from randomization (Visit 3) to the date of Visit 29. For a subject lost to follow-up, this will be defined as the time from randomization to the time point after which an exacerbation could not be assessed (i.e., the last contact date).

Exacerbations that occur after a subject has discontinued IP should still be accounted for when deriving the total number of exacerbations; and likewise, the follow-up time will reflect the follow-up time regardless of whether or not the subject is still on IP.

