7. Additional maintenance asthma controller medications are allowed according to standard practice of care. These medications must be stable for 3 months prior to enrolment (Visit 1). Furthermore, after randomization, the subject's background maintenance medication for asthma shall remain unchanged throughout the study.
8. At Visit 1 the subject must have a morning pre-BD FEV1 value <80% (<90% for subjects 12 to 17 years of age) of their predicted normal value (PNV). At Visit 2 the subject must have a morning pre-BD FEV1 value of  $\geq 40$  and <80% value (<90% for subjects 12 to 17 years of age) of their PNV. If this is not met at Visit 2, it must be met at Visit 3. Prior to the lung function measurement, the subject should withhold their BD for the effect duration specific to the BD.
9. A post-BD reversibility in FEV1 of  $\geq 12\%$  and  $\geq 200$  mL at Visit 2. If not met at Visit 2, it must be met at Visit 3 (randomization). Before reversibility testing, the subject should withhold their BD for the effect duration specific to the BD.
10. At least 2 documented asthma exacerbations in the 12 months prior to the date informed consent is obtained that required use of a systemic corticosteroid. In case of subjects who are re-screened within 30 days of their screen failure date; the 12 months can be calculated from the date that the first informed consent was obtained.

The below defines what is acceptable to document exacerbations in this Program:

1. Discharge summaries from a hospital, emergency department, or an urgent care facility indicating that a subject was hospitalized/treated with systemic steroids for an asthma exacerbation.
2. Signed and dated notes from a referring physician, including information regarding diagnosis and treatment of an exacerbation with systemic steroids.
3. Subjects can provide evidence of prescriptions for systemic steroids used during an exacerbation.
4. A documented conversation between the treating/referral physician or nurse/nurse practitioner certifying that a subject was treated for an exacerbation with steroids at their clinic or under their supervision. The dates (month/year) of the exacerbations and verbal confirmation that appropriate prescriptions were provided is necessary. This option should be used only if reasonable attempts to procure subject records have been unsuccessful.

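### Does the objective-support rule in Section 5.1.1 drop off-treatment exacerbations in subjects who are followed only by a Week 52 contact?

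*Protocol*

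**What the plan says.** Section 5.1.1 sets two steps for an event with weak confirmation. If none of the pre-specified measurements deteriorated, "the Investigator will have to justify the decision for defining the event as an exacerbation". Below that lies a floor: "Events that are not supported by any objective assessment will be deemed not to be a protocol-defined exacerbation".

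Section 4.2 offers three kinds of follow-up after treatment stops. In option 3 the subject is contacted at 52 weeks, and "No other study assessments will be performed prior to this contact". The section also says, for options 2 and 3, that "they will complete the IP Discontinuation visit immediately and then a follow up telephone call at week 52". Exacerbation information and changes in concomitant medication must still be collected at that contact.

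Section 5.1.1 then covers off-site and off-treatment events: "A copy of the medical record should be obtained for exacerbations evaluated and treated at non-study sites"; "Exacerbations that occur after a subject has discontinued IP should still be accounted for when deriving the total number of exacerbations"; and "the follow-up time will reflect the follow-up time regardless of whether or not the subject is still on IP". Section 8.5.6 uses the log of that time as the offset. Section 8.5.2 acknowledges that objective confirmation is weaker after discontinuation and names an analysis excluding those data.

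**The concern.** An option 3 subject has no diary, home peak flow, spirometry or study examination after the discontinuation visit. If objective support could come only from those sources, every later event would fail the floor while the subject's time stayed in the denominator. That arm's rate would be understated, contrary to the stated aim of using all data regardless of discontinuation (Section 8.5).

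Nothing in Section 5.1.1 says in terms that an outside record or a prescription is objective support. Prescriptions are accepted in inclusion criterion 10 ("Subjects can provide evidence of prescriptions for systemic steroids used during an exacerbation"), but for the history before consent. Adjudication (Section 6.8.1) lists ER or urgent care visits, hospitalizations and deaths, so a course of steroids alone gets no such second review. The two sentences on weak confirmation can also look contradictory: one lets the investigator justify an event, the next disallows it.

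At stake is the count behind the primary rate ratio. Option 3 is the subject's own choice after stopping, so equal uptake in the two arms is not assured.

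**Working it through.** **Reading the text**

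1. The two sentences in Section 5.1.1 form two tiers. The first concerns the pre-specified measurements: an event outside them needs justification. The second concerns events with no objective assessment of any kind. An event can fail the first test, be justified, and still pass the second.
2. The floor is not limited to study assessments. Section 5.1.1 describes worsening by symptoms or signs, including physical examination and lung function, and allows it to be subject-driven. An examination by a primary care physician or in an emergency department fits that description.
3. The section asks for the outside record, has its details entered in the exacerbation module, and says that off-treatment events count. Those instructions would serve little purpose if outside records could not support an event.
4. A subject lost to follow-up contributes time only to the last contact. Full time is kept when the subject is still followed, and at the Week 52 contact exacerbations are asked about.

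What remains exposed is a post-discontinuation steroid course whose outside record contains no symptoms, examination or lung function.

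**The plan's own figures (Section 8.2)**

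Inputs: placebo rate 0.8, dispersion 0.95, 770 subjects, uniform 15% loss, about 355 subject-years per group, biomarker positive share 20% to 35%.

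- Subject-years: 770 × (1 − 0.15/2) = 712, or 356 per group (stated: about 710 and 355).
- Var(log RR) = (1/m₀ + 1/m₁ + 2 × 0.95)/T; power = Φ(|log RR|/SE − z).
- All subjects, 37% reduction, two-sided 1%, T = 355: 89.7% (stated: at least 90%).
- Biomarker positive, 50% reduction, two-sided 5%: T = 0.20 × 355 = 71 gives 0.690; T = 0.35 × 355 = 124.25 gives 0.902 (stated: 70% to 90%).

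The stated figures are reproduced within rounding.

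**Illustration**

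Assumed, because the protocol gives none of these: share *s* of an arm in option 3, half a year remaining on average, share *d* of their off-treatment events disallowed. Events retained = 1 − 0.5·s·d.

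*Unequal uptake (10% v 5%), same rate ratio on and off drug:*

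| d | More option 3 on active | More on placebo |
|---|---|---|
| 1 | 0.95/0.975 = 0.974 | 1.026 |
| 0.5 | 0.975/0.9875 = 0.987 | 1.013 |
| 0.25 | 0.9875/0.99375 = 0.994 | 1.006 |

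*Equal uptake (10% each), same rate ratio on and off drug, d = 1:* the ratio is unchanged and 5% of events are lost. With rates 0.76 v 0.38 in place of 0.80 v 0.40, power falls from 0.690 to 0.676 (20% share) or from 0.902 to 0.892 (35%).

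*Equal uptake (10% each), rate ratio 0.50 on drug and 1.0 off drug:* the true all-data ratio is 0.95 × 0.5 + 0.05 × 1.0 = 0.525.

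- d = 1: 0.475/0.95 = 0.500
- d = 0.5: 0.500/0.975 = 0.513
- d = 0.25: 0.5125/0.9875 = 0.519

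So equal losses leave the ratio unchanged only if the effect is the same on and off drug.

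*Most adverse case tried:* 15% on active, 5% on placebo, effect fully lost after stopping. The true ratio is 0.925 × 0.5 + 0.075 = 0.5375. It is counted as 0.4625/0.975 = 0.474 if every off-treatment event is disallowed, and as 0.51875/0.99375 = 0.522 if a quarter are.

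**The case for a change.** The strongest case for a change is that Section 5.1.1 fixes the primary event definition, site staff apply it directly, and one sentence would settle what counts. Excluding post-discontinuation data (Section 8.5.2) answers a different question and does not say which events belong in the primary count. If the effect fades off drug, the loss favours tralokinumab even with equal uptake.

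Much of this stands. The protocol does not state the documentation rule, the sensitivity analysis does not define the primary count, and the direction under a fading effect is as described. But the large shifts need every off-treatment event to be disallowed, and the text does not do that: emergency, hospital and primary care events with a recorded examination meet the floor.

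The obvious remedy also has a price. Accepting a prescription alone as support in option 3 would set a looser endpoint standard for one self-selected kind of follow-up, while the same course on treatment, or under options 1 and 2, would still need an objective assessment. A prescription shows treatment, not worsening. If option 3 uptake differed by arm, ascertainment would then differ by arm, which is the very problem to be avoided.

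**Conclusion.** No change follows. The two sentences in Section 5.1.1 do not contradict each other, outside records are sought, and off-treatment events are meant to count. What is left is an unwritten rule for a narrow group of poorly documented steroid courses, which the analysts, the SAP (not available here) or the data-entry instructions can settle sensibly, blind to treatment.

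The size is unknown because the protocol gives no option 3 uptake. If a quarter of off-treatment events were disallowed, the ratio would be multiplied by 0.994 or 1.006 at 10% v 5% uptake. With 10% in each arm and an effect lost on stopping, 0.525 would be counted as 0.519. Shifts such as 0.525 to 0.500, or 0.5375 to 0.474, need all off-treatment events to be disallowed, which the text does not support. The conclusion rests on reading the floor as any objective assessment, wherever it was made, and on outside records usually containing some clinical finding.
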